9.3. Data Analysis Considerations

9.3.1. Analysis Populations

The intent-to-treat (ITT) population is defined as all randomized subjects who received at least one dose of study drug. Subjects will be assessed according to the treatment they are randomised to. This population will be the primary analysis population for efficacy analysis. Additional output(s) may be provided if subjects are mistakenly treated but not randomized to support safety tables.

The Subset ITT population (2 to 6 years old) is defined as a subset of ITT population comprising subjects aged ≥ 2 to ≤ 6 years old.

The per protocol (PP) population is defined as all randomized subjects in ITT population who do not have any full protocol deviations. This population will be used for supportive analysis of the primary efficacy endpoint only. These detailed criteria of full protocol

deviations will be defined in the Reporting and Analysis Plan (RAP). The PP population will not be analyzed if this population comprises more than 95% or less than 50% of the ITT population.

All the summary and analysis will be performed for both ITT population and Subset ITT population (2 to 6 years old). Both the ITT, Subset ITT and PP populations will be determined prior to unblinding of the study.

9.3.2. Interim Analysis

There are no interim analyses planned for this study.

9.4. Key Elements of Analysis Plan

Where possible, data from subjects who withdraw prematurely from the study will be included in any analyses. In general, the minimum data required will be a baseline evaluation (if baseline is needed for analysis) and at least one post-baseline evaluation.

TNSS for each assessment time point is the sum of the 4 individual nasal symptom scores (rhinorrhea, nasal congestion, nasal itching and sneezing), ranging from 0 to 12, since each of the four individual symptoms will be scored on a four-point scale from 0 to 3. rTNSS is the symptom score which documented in a reflective manner (represents how the subjects has been feeling over the preceding 12 hours).

The daily rTNSS will be computed as the average of the PM rTNSS and the AM rTNSS of the next day, based on the assessments prior to dosing. For example, the Day 1 rTNSS will be computed as: $[(\text{PM rTNSS})_{\text{Day 1, first day of dosing}} + (\text{AM rTNSS})_{\text{Day 2, prior to second dosing}}]/2$.

If for a given subject and at a given assessment time (i.e., AM or PM) any of the four symptoms are missing, then the rTNSS will be considered missing for that assessment time. If one (but not both) of the AM and PM rTNSS is missing for a given day (e.g., a dosing interval during the treatment period), the non-missing rTNSS for that day will be used as the rTNSS for the day.

The baseline period for diary card endpoints is defined as 4 days prior to randomization, including the AM symptom assessment on the randomization (i.e., treatment initiation) date. Day 1 assessments include the PM assessment on the randomization (i.e., treatment initiation) date and the AM assessment of the day after treatment initiation. The first 2-week treatment period is defined as the first 14 dosing (24-hour) days of the treatment period. Baseline values for other endpoints will be those used as appropriate from either Visit 1 (Screening) or Visit 2 for clinic visit.

Endpoints relating to daily diary assessments will be calculated from all available data over the period of interest. The mean value over the period refers to the mean of the non-missing values of each endpoint during the period. No imputations will be performed on missing daily diary data.

Means, standard deviation, median, minimum, and maximum will be given for the summary of continuous variables and frequencies and percentages will be given for the summary of categorical variables.

In each efficacy analysis table, sample size, least square mean, standard error of the least square mean, least square mean difference, 2-sided p-values and 2-sided 95% CIs (whenever appropriate) for all pair wise comparisons will be given but no inference will be drawn. All the results from analysis modeling are for descriptive purpose.

No multiplicity adjustments are necessary since no formal hypothesis test will be done.

Appropriate graphs will be reviewed as part of the model checking process to ensure that distributional assumptions hold. In all cases, if any assumptions of the proposed method of analyses are not met, alternative methods (i.e., nonparametric methods) of analyses will be used.

9.4.1. Primary Analyses

The primary efficacy endpoint is the mean change from baseline over the first 2 weeks treatment period in daily rTNSS (rhinorrhea, nasal congestion, nasal itching and sneezing), as evaluated on a 4-point categorical scale. The minimum data required for the primary endpoint analysis will be 4 days daily rTNSS data in baseline period and at least 4 days daily rTNSS data in the first 2 week treatment period after randomisation.

The primary analysis method will be the pair wise comparison of treatment groups (active vs. placebo) using analysis of covariance (ANCOVA) adjusting for baseline daily rTNSS, classification of AR (IAR or PER), age, gender and treatment.

Mean daily rTNSS and mean change from baseline in daily rTNSS will be summarized by week (over each week) as well as over the first 2 weeks (14 days) of treatment period and over the entire treatment period (28 days) by treatment group.

The change from baseline in daily rTNSS over Week 1, Week 2, Week 3, and Week 4 will also be analyzed. The analysis results of changes over Week 1, Week 2 will be used to reinforce the robustness of the primary efficacy endpoint.

All graphs, summary and analysis tables will be provided for the ITT population (of primary interest), PP population (supportive if appropriate) and the subset ITT- ≥ 2 to ≤ 6 years population (supportive).

For the modeling analysis on ITT- ≥ 2 to ≤ 6 years population, if the statistical model does not converge for all the covariates, sex, age will be dropped from the model. If the model still does not converge, then classification of AR (IAR or PER) will be further dropped. The details will be included in the RAP.

Some of summary tables will also be repeated for the subgroup by classification of AR and age category.

9.4.2. Secondary Analyses

Regarding the secondary analyses for diary card endpoints (rTOSS and rTNSS over 4 weeks), the analysis method will be the same as the primary efficacy analysis..

Overall evaluation of response to therapy for subjects who are in the ITT population will be summarized, and analyzed using logistic regression adjusting for age, gender, classification of AR (IAR or PER), and treatment.

ANCOVA model adjusting for baseline nasal finding score by anterior rhinoscopy, classification of AR (IAR or PER), age, gender and treatment will be used to analyze nasal finding score by anterior rhinoscopy.

ANCOVA model adjusting for classification of AR (IAR or PER), age, gender and treatment will be used to analyze the mean rescue-free days over the first 2 weeks and over the 4 week treatment.

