5.3. Randomisation Criteria

[1] At Visit 2, the Subject must continue to meet the inclusion/exclusion criteria above. In addition the subject must meet the following criteria:

- a. On the morning of Visit 2, subjects must have nasal or/and ocular symptoms.
- b. Average of the last 8 rTNSS assessments (4 AM assessments, 4 PM assessments) over the consecutive four 24-hours periods prior to randomization must be ≥ 6 . This includes the AM assessment on the morning of Visit 2.
- c. Average of the 8 reflective nasal symptom assessments for congestion (4 AM assessments, 4 PM assessments) over the consecutive four 24-hour periods prior to randomization must be ≥ 2 . This includes the AM assessment on the morning of Visit 2.

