6.9.1. Permitted Medications and Non-Drug Therapies

Loratadine syrup, an on-the-count antihistamine, will be provided as rescue medication on only an as needed basis during the treatment period of the study. At Visit 2 after randomization, subjects will be dispensed rescue medication. The subject (and/or subject's parent/guardian) will record their daily use of allergy rescue medication, not to exceed **1 teaspoon (5 mL) with weight ≤30 kg or 2 teaspoon (10 mL) with weight >30 kg** a day. The use of rescue medication should be in accordance with the instructions provided with the medication.

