7.4.4. Overall evaluation of Response to therapy by investigator

The investigator will evaluate subject's overall response to therapy (improvement in the symptoms of AR) compared with Visit 2, in accordance with the Time and Event Table, using 7 point categorical scale below and record it in the CRF.

1. Significantly Improved
2. Moderately Improved
3. Mildly Improved
4. No Change
5. Mildly worse
6. Moderately worse
7. Significantly worse

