8.1.2. Planned Efficacy Statistical Analyses

Primary Statistical Analyses
Endpoint(s)

 • Overall evaluation of response to therapy (evaluated on a 7-point categorical scale) after the first 2 weeks treatment (day 15) • The mean change from baseline of study intranasal finding score by anterior rhinoscopy at the first 2 weeks treatment (day 15) • Mean change from baseline over the first 2 weeks treatment period in the daily reflective total ocular symptoms score (rTOSS) • Rescue loratadine use (mean rescue-free days) over the first 2 weeks treatment period • Overall evaluation of response to therapy after 4 weeks treatment period (day 29) • The mean change from baseline of intranasal finding score by anterior rhinoscopy at the end of treatment (day 29) • Mean change from baseline over the 4 weeks treatment period in the daily rTOSS • Rescue loratadine use (mean rescue-free days) over the entire 4 weeks treatment period
Model Specification

 • Overall evaluation of response to therapy (evaluated on a 7-point categorical scale) after the first 2 weeks treatment and 4 weeks will be analyzed using a logistic regression. • Terms fitted in the logistic regression model will be included: Treatment, classification of AR (IAR or PER), gender, age (as continuous variable). • For the Rescue loratadine use (mean rescue-free days) will be analyzed using an ANCOVA analysis • Terms fitted in the ANCOVA model will be included: 
 Fixed Categorical Covariates :Treatment, classification of AR (IAR or PER), gender Fixed Continuous Covariates : age • For the secondary endpoints of rTOSS and nasal finding score by anterior rhinoscopy will be analyzed using an ANCOVA analysis. • Terms fitted in the ANCOVA model will be included: 
 Fixed Categorical Covariates :Treatment, classification of AR (IAR or PER), gender Fixed Continuous Covariate : Baseline value of endpoint, age
Model Checking & Diagnostics

 • Refer to Appendix 12: Model Checking and Diagnostics for Statistical Analyses.
Model Results Presentation

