11.12. Appendix 12: Model Checking and Diagnostics for Statistical Analyses

11.12.1. Statistical Analysis Assumptions

Endpoint(s)	
 • Mean change from baseline of daily rTNSS over each week • Mean change from baseline of daily rTNSS over the first 2 weeks treatment • Mean change from baseline of daily rTNSS over the 4 weeks treatment
Analysis	
 • ANCOVA 
• Model assumptions will be applied, but appropriate adjustments may be made based on the data.
 
• Distributional assumptions underlying the model used for analysis will be examined by obtaining a normal probability plot of the residuals and a plot of the residuals versus the fitted values (i.e. checking the normality assumption and constant variance assumption of the model respectively) to gain confidence that the model assumptions are reasonable.
 
• If there are any departures from the distributional assumptions, alternative models will be explored.
 
• The following SAS code will be used:
 <pre>proc mixed data= adef; by week; class treatment gender iarper; model endpoint=treatment baseline gender age iarper; lsmeans treatment / cl diff e om; ods output lsmeans=lsmeans; ods output diffs=diffs; run;</pre>

Endpoint(s)	
 • Overall Evaluation of Response to Therapy
Analysis	
 • Logistic Regression Model 
• Model assumptions will be applied, but appropriate adjustments may be made based on the data.
 
• The following SAS code will be used:
 <pre>proc logistic data=adef descending; by week; class treatment (ref='1') gender iarper / param=ref;</pre>

```
model respond=treatment gender age iarper / clodds=wald expb;

ods output oddsratios=odds1

      (where=(index(effect,'TREATMENT')>0
      or index(effect,'treatment')>0));

ods output parameterestimates=pval1

      (keep=probchisq variable classval0
      where=(variable in ('TREATMENT','treatment')));

ods output Type3=pval2

      (where=(variable in ('TREATMENT','treatment')));

run;
```

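### The models for rescue-free days and overall response adjust for no measure of starting symptom severity, although baseline daily rTNSS is needed for randomisation and is already in the primary model

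*Protocol*

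**What the plan says.** Protocol 9.4.2 sets two secondary models without a baseline score.

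- **Rescue-free days, first 2 weeks and 4 weeks:** "ANCOVA model adjusting for classification of AR (IAR or PER), age, gender and treatment will be used to analyze the mean rescue-free days".
- **Overall response, days 15 and 29:** to be "analyzed using logistic regression adjusting for age, gender, classification of AR (IAR or PER), and treatment".

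The SAP agrees. SAP 1 repeats both models. SAP 8.1.2 states: "Terms fitted in the logistic regression model will be included: Treatment, classification of AR (IAR or PER), gender, age (as continuous variable"). The code in SAP 11.12.1 is "model respond=treatment gender age iarper / clodds=wald expb". SAP 8.1.1 applies the secondary analyses to ITT and to the 2-to-6 subset.

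The other efficacy models do carry a baseline. The primary ANCOVA in Protocol 9.4.1 is fitted "adjusting for baseline daily rTNSS, classification of AR (IAR or PER), age, gender and treatment", and the rTOSS and rhinoscopy models each include their own baseline value.

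Three further points bear on this:

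- Protocol 5.3 makes the baseline score a condition of entry: "Average of the last 8 rTNSS assessments (4 AM assessments, 4 PM assessments) over the consecutive four 24-hours periods prior to randomization must be" at least 6.
- Protocol 4.1 stratifies by age group and AR class, not by symptom intensity.
- Rescue-free days have no baseline of their own, because Protocol 6.9.1 says: "At Visit 2 after randomization, subjects will be dispensed rescue medication".

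**The concern.** Neither the randomisation nor these two models takes account of how severe a child's symptoms were at the start. AR class does not stand in for this, since Protocol 5.1 defines it by days per week or weeks with symptoms, not by intensity. A child who starts with more symptoms may well take rescue more often, and may have more room to improve.

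If so, the rescue-free-days comparison has a wider interval than it needs, and part of any chance severity difference between arms carries into the estimate. For overall response, the conditional treatment effect is understated. Protocol 9.4 plans estimates, confidence intervals and p-values for the efficacy models. In a trial without formal tests, the precision and comparability of these estimates are what the reader has to go on. Chance imbalance is largest in the 2-to-6 subset, which the protocol names as a subgroup of interest.

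**Working it through.** **1. The plan's own figure.** No precision is stated for these four results. The stated half-widths concern the primary endpoint (Protocol 9.2.1, SD 2.6) and use t(0.975, 2n−2) × SD × √(2/n). They reproduce as 0.725 at 100 per arm and 1.032 at 50 per arm. This point does not alter them.

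**2. Inputs.** From Protocol 9.2.1: 100 evaluable per arm, and 50 per arm aged 2 to 6. There are three arms, so N = 300 or 150. The documents give no correlation r between baseline rTNSS and either outcome. The values below are assumptions, with r read as the correlation left after the planned covariates.

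**3. Rescue-free days: standard error.** The ratio of SE with baseline to SE without it is about √[(1 − r²)(1 + 1/(N − 8))]. For r = 0.3 and N = 300 this is √(0.91 × 1.00342) = 0.956.

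| r | SE ratio, 100 per arm | SE ratio, 50 per arm | Equivalent extra subjects, 1/(1 − r²) − 1 |
|---|---|---|---|
| 0 | 1.002 | 1.004 | 0% |
| 0.1 | 0.997 | 0.999 | 1% |
| 0.2 | 0.982 | 0.983 | 4% |
| 0.3 | 0.956 | 0.957 | 10% |
| 0.5 | 0.868 | 0.869 | 33% |

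Simulated least-squares fits at 100 per arm (1,000 runs per setting) gave ratios of 0.997, 0.956 and 0.868 at r = 0.1, 0.3 and 0.5.

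**4. Rescue-free days: chance imbalance.** The difference in mean baseline between two arms, in baseline SDs, has standard deviation √(2/n).

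- 100 per arm: 95% limit 1.96 × 0.141 = 0.28 SD. A difference above 0.25 SD has probability 8%.
- 50 per arm: 95% limit 1.96 × 0.200 = 0.39 SD. A difference above 0.25 SD has probability 21%.

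The shift in the outcome difference is r times the imbalance. At r = 0.3 and the 95% limit it is 0.3 × 0.277 = 0.08 outcome SD (100 per arm) or 0.3 × 0.392 = 0.12 (50 per arm).

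**5. Overall response.** The scale has seven points and the plan defines no dichotomy, so both forms were simulated.

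Binary response, two arms of 100, assumed conditional log OR 0.6, 2,000 runs per setting:

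| Log OR per baseline SD | Mean log OR, without → with | SE, without → with | Power, without → with |
|---|---|---|---|
| 0.3 | 0.588 → 0.604 | 0.291 → 0.296 | 0.55 → 0.54 |
| 0.6 | 0.560 → 0.608 | 0.290 → 0.304 | 0.51 → 0.52 |
| 1.0 | 0.490 → 0.602 | 0.289 → 0.321 | 0.42 → 0.47 |

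Proportional odds, three arms of 100, assumed log OR 0.7, baseline effect 0.3 / 0.6 / 0.9 per SD, 120 to 150 runs per setting: adding baseline raised the squared test statistic by about 3–4% / 10–16% / 22–28%. The log OR without baseline was about 2% / 6–8% / 11–13% smaller. The SE was unchanged or rose slightly (for example 0.253 to 0.255 at 0.6).

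In both forms, any gain comes from a larger conditional estimate, not from a smaller SE.

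**The case against.** The strongest reply is that this is a consistent design choice. Protocol and SAP agree, and the rule appears to be to adjust for an endpoint's own baseline where it has one. Both models keep the AR-class stratification factor, age and gender. The endpoints are secondary and the trial is declared descriptive. All of that stands, and it limits the importance of the point.

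The size also rests wholly on assumed prognostic strength. The entry floor of 6 on a 12-point scale, with mean congestion of at least 2, narrows the baseline range and may weaken the correlation. Overall response is rated "compared with Visit 2, in accordance with the Time and Event Table, using 7 point categorical scale below", so starting severity is partly built in. Even the sign of its link with baseline is open: more room to improve, or more resistant disease. This too stands.

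Three stronger readings are tempting but not supported:

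- A reader might infer that all four results are noisier. That fits only the two rescue-free-days results, and only if baseline predicts rescue use.
- A reader might infer that severity imbalance biases the comparison or passes into it in full. It is scaled by the outcome slope. Randomisation keeps the rescue-free-days comparison unbiased on average, and its interval already allows for chance imbalance.
- A reader might treat the smaller odds ratio as an error. It answers a less conditional question. SAP 8.1.2 lists only frequencies, percentages and p-values for this model, although the code in SAP 11.12.1 outputs odds ratios.

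None of this shows a material cost to adding the term: with no correlation the SE rises by about 0.2% at 100 per arm.

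**Conclusion.** The omission is clear in both documents, and the covariate is at hand. Including it is a low-cost improvement to secondary, descriptive analyses. The planned comparisons are not invalid, and no stated figure changes.

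For rescue-free days the gain is negligible if r is 0.1, about 2% of the SE at 0.2, and 4% to 13% for r from 0.3 to 0.5. Adjustment also protects against a shift of about 0.08 outcome SD (100 per arm) or 0.12 (50 per arm) at r = 0.3 and the 95% limit of imbalance. For overall response, omission attenuates the conditional odds ratio and modestly weakens the test if baseline is prognostic; with a weak link there is little or nothing to gain. These sizes depend on the assumed correlations and effects, which the documents neither give nor rule out.

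**What to change.** Before unblinding, add baseline daily rTNSS as a continuous covariate to the rescue-free-days ANCOVA and the overall-response logistic model, at 2 and 4 weeks, for ITT and Subset ITT. The places are Protocol 9.4.2 and SAP 1, 8.1.2 and 11.12.1. In 11.12.1 the logistic model statement gains one term; no code for rescue-free days is shown there, so it should be added. State that any odds ratio reported is conditional on the covariates. Say also where the new term stands in the order for dropping covariates in SAP 11.10, which now names only sex, age and AR class. If the sponsor prefers to keep the planned models as the main ones, the adjusted versions could be pre-specified as sensitivity analyses.

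The cost is one degree of freedom per model. A child with no usable baseline score would drop out of these analyses, since covariates are not imputed (SAP 11.7.2), but the entry criterion should make that rare.

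While editing, correct the titles of SAP Tables 2.17 and 2.18. They refer to change from baseline in rescue use, but rescue is first dispensed after randomisation, so there is no baseline value to change from.

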9.4.3. Other Analyses

Safety analysis

Safety data will be summarized and/or listed by treatment group for the ITT population.

Extent of Exposure

The extent of exposure to study drug will be summarized by treatment group.

Adverse Events (AEs)

AEs will be coded using the standard GSK dictionary, MedDRA, and grouped by body system. AEs occurring pre-treatment, during active treatment and post-treatment will be summarized separately. The number and percentage of subjects experiencing at least one AE of any type, AEs within each body system and AEs within each preferred term will be presented for each treatment group. Separate summaries will be provided for all AEs, drug related AEs, SAEs, and for AEs leading to withdrawal.

Clinical Laboratory Evaluations

Clinical laboratory evaluations, including hematological and clinical chemistry, will be summarized by treatment group for each visit. Further details will be provided in the RAP.

Nasal Examinations

Nasal examinations will be performed at each visit, and will include assessments of nostril patent, septum, mucosa, secretions, ulcers, and polyposis. Nasal examination results will be summarized by visit for each of the 6 examination parameters listed above. At all visits, frequencies of classifications (yes/no, absent/present) will be calculated. Shift from baseline (Visit 2) will be summarized for each individual nasal examination parameter. Abnormal nasal examination results will be listed.

Vital Signs Assessments

Vital signs will be summarized for each clinic visit. Further details will be provided in the RAP.

Deaths and SAEs

All SAEs will be tabulated and listed by treatment group. Deaths and SAEs will be documented in case narrative format.

10. STUDY GOVERNANCE CONSIDERATIONS**10.1. Posting of Information on Publicly Available Clinical Trial Registers**

Study information from this protocol will be posted on publicly available clinical trial registers before enrollment of subjects begins.

